9.2.1 Primary Endpoint

The primary endpoint of this study is OsciPulse device tolerability compared to the current standard of care device. This endpoint will be measured by quantifying the differences in the responses to the questions on the subject questionnaire for each device. We will compare the visual analog scale ratings for the first 4 questions for each subject between the OsciPulse device and the reference therapy device. There are also 4 questions on the 6-hour questionnaire that ask the participants to directly compare the two devices, to determine the difference in tolerability. The ratings are reported in millimeters and the average differences between the responses will be statistically evaluated using a paired t-test.

9.2.2 Secondary Endpoints

The secondary endpoints of this study are the hemodynamic effects of each device on venous return dynamics. The hemodynamic endpoints will result from vascular ultrasound measurements

These hemodynamic parameters will be averaged across subjects and the difference between the measurements for each device will be evaluated using a paired t-test. The hemodynamic data will demonstrate the efficacy of the OsciPulse device to create the desired valve sinus reversing flow profile that has been shown in previous clinical studies with healthy volunteers. Confirming this flow in the subject population will demonstrate that the OsciPulse device can be successfully deployed in the clinical setting by clinical staff.

Safety will be monitored by tracking all adverse events during the 3-hour period of wearing each device and evaluated by determining the total number of events under each condition.

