Statistical Methodology	Part1: Device tolerability will be assessed with a questionnaire focused on the comfort of the OsciPulse device. This data will only be used to validate the tolerability of the device for use in Phase 2 so no statistical analysis will be performed. Part 2: Device tolerability will be measured with a subject questionnaire focused on their comfort for both the OsciPulse device and the intermittent pneumatic compression device. The questions will have continuous visual analog scales to gauge responses, and we will use a paired t-test to evaluate the difference in responses between the OsciPulse device and the reference therapy. We will also monitor subject compliance, and venous valve sinus hemodynamics, when feasible, for each device and a paired t test will be used to compare those values.
Safety Evaluations	Part 1: Adverse events will be collected

Part 2: Adverse events will be collected. Expected AEs in this population include VTE, skin ulceration, peripheral nerve palsy, limb ischemia, and falls.

**Data and Safety
Monitoring Plan**

The Sponsor is responsible for monitoring the data quality and the ongoing safety of subjects.

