9.2.4 Statistical Methods

The statistical approach to analysis will be to use paired t-tests to evaluate the difference between the standard of care cleared intermittent pneumatic device and the OsciPulse device using a

paired t-test. We will evaluate the primary endpoint of tolerability through quantification of the difference between the visual analog scale markings on the patient questionnaire for each device. We will also use a paired t-test to evaluate the changes in venous flow that occur in each patient during use of both devices.

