9.2.6 Efficacy Analysis

Efficacy will be scored by the ultrasound measurements of venous blood flow during the use of the OsciPulse device and reference therapy device. Ultrasound measurements during device action will provide quantification of centerline venous flow velocity, the amount of flow within the sinus of the valve at the sapheno-femoral junction, and the amount of reversing flow in the sinus of the sapheno-femoral junction valve. Measurements may be taken at other vascular sites if the visualization window is not of sufficient quality for data collection at the sapheno-femoral junction. These measurements will be compared for each device and difference for each individual patient will be quantified and a paired t-test will be used to evaluate the overall efficacy.

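### The paired OsciPulse–IPC test does not by itself establish that OsciPulse creates reversing valve-sinus flow, which Section 9.2.2 says the scans will demonstrate

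*Combined protocol and SAP*

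**What the plan says.** Section 9.2.2 states what the ultrasound data will show: "The hemodynamic data will demonstrate the efficacy of the OsciPulse device to create the desired valve sinus reversing flow profile". It then builds a second conclusion on the first: "Confirming this flow in the subject population will demonstrate that the OsciPulse device can be successfully deployed in the clinical setting by clinical staff". Both concern OsciPulse on its own.

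The analysis described for these data compares the two devices:

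- Section 9.2.2: "These hemodynamic parameters will be averaged across subjects", and "the difference between the measurements for each device will be evaluated using a paired t-test".
- Section 9.2.6: "difference for each individual patient will be quantified and a paired t-test will be used to evaluate the overall efficacy". The measurements named there are those taken while the device is acting.
- Study Summary, Statistical Methodology: "venous valve sinus hemodynamics, when feasible, for each device and a paired t test will be used to compare those values".
- Section 9.2.4 is less clear: "We will also use a paired t-test to evaluate the changes in venous flow that occur in each patient during use of both devices". This could mean change from rest under each device, or the difference between devices. The opening sentence of that section frames the tests as IPC against OsciPulse.

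Section 8.5 has the parameters measured at rest and during inflation, for both devices. The Part 2 objective in Section 3.2 is comparative with IPC. Section 9.3 limits analysis to subjects who had both exposures and completed the required questionnaires and scans.

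**The concern.** The promised conclusion is absolute (OsciPulse produces a given flow pattern in these patients), while the clearly planned test is relative (OsciPulse minus IPC). The two agree only when IPC leaves reversing flow close to its resting level, and the plan does not say that it does.

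At stake is the only efficacy statement in the trial, and the deployment claim that rests on it. A null comparison could be read as failure when the device works. A positive one could be read as proof that the device creates the flow when no comparison with rest has been made.

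**Working it through.** **The plan's own figure.** Section 9.2.3 allows for 6 losses among 20 enrolled: 20 − 6 = 14. This reproduces. It counts subjects with tolerability and safety data. Scans are done only where feasible, so the number of scan pairs may be lower. The plan gives no alpha, power, effect size, SD or margin for the hemodynamic endpoints, so there is no power figure to reproduce.

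**Assumptions for the check.** Two-sided 5% level. Reversing flow in arbitrary units, SD 1 in each condition, within-subject correlation 0.5. The SD of a paired difference is then √(1 + 1 − 2 × 0.5) = 1. Simulation of 20,000 trials, n = 14.

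| True means (rest, OsciPulse, IPC) | OsciPulse − IPC | OsciPulse − rest |
|---|---|---|
| Both raise flow equally (5, 6, 6) | significant in about 5% | positive in 93% |
| Neither raises flow (5, 5, 5) | significant in about 5% | significant in about 5% |
| IPC raises flow more (5, 6, 7) | favours IPC in 93% | positive in 93% |
| OsciPulse no effect, IPC lowers flow (5, 5, 4) | favours OsciPulse in 93% | significant in about 5% |
| Only OsciPulse raises flow (5, 6, 5) | favours OsciPulse in 93% | positive in 93% |

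With n = 20 the 93% entries become about 99% and the 5% entries do not move. The 5% in the first two rows is the type I error rate and does not depend on the assumed effect size. Those rows give the same between-device result although OsciPulse works in one and not in the other. The fourth row is a logical possibility; the documents do not say whether IPC lowers reversing flow.

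**What an OsciPulse-against-rest analysis could deliver.** Power of a paired t-test (noncentral t) by standardized change:

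| n | 0.5 | 0.8 | 1.0 | Change detectable with 80% power |
|---|---|---|---|---|
| 8 | 23% | 50% | 68% | 1.16 |
| 14 | 41% | 79% | 93% | 0.81 |
| 20 | 56% | 92% | 99% | 0.66 |

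For n = 14 the 95% interval for the mean change has half-width 2.160 × SD/√14 = 0.58 SD.

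For a proportion, if all n scanned subjects meet a criterion, the exact 95% lower bound is 0.025^(1/n): 63% for 8/8, 77% for 14/14, 83% for 20/20.

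**What pairing costs.** The OsciPulse question needs no IPC scan. Suppose each scan is feasible with probability p, independently (an assumption). Of 14 subjects, 14p have an OsciPulse scan and 14p² have both:

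- p = 0.5: 7.0 against 3.5
- p = 0.7: 9.8 against 6.9
- p = 0.9: 12.6 against 11.3

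If the two scans always succeed or fail together, nothing is lost.

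**The case against.** The strongest defence is that the paired test fits the comparative objective in Section 3.2, and that the sentence in Section 9.2.2 is an expectation for a secondary endpoint in a convenience sample, not a decision rule. That is fair, and it limits the weight of the point. It does not make the sentence follow from the test.

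A reader might infer several stronger things that the documents do not support:

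- **That the comparison can neither confirm nor refute the claim.** The endpoint in Section 4.6.2 is a volume. If it cannot be negative, OsciPulse above IPC implies a mean above zero on OsciPulse. That supports the presence of some reversing flow, though not an increase over rest. The planned averages are also descriptive evidence.
- **That it is the only planned test.** Section 9.2.4 may intend change from rest, Section 4.6.2 speaks of a change at least for velocity, and the resting values are collected.
- **That a significant result could mislead because few subjects respond.** If 6 of 15 show an identical response on OsciPulse, and all other values are zero, then t = √(6 × 14/9) = 3.06, p = 0.009. But OsciPulse would then truly create the flow in six subjects and raise the mean. This is an error only under a most-subjects standard, which the plan does not set.
- **That Section 9.2.2 rests on reversing flow alone while Section 9.2.6 merges three measures into one verdict.** The parameter list in Section 9.2.2 appears to be missing from the public text, and the overall efficacy in Section 9.2.6 may simply mean across patients.

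A criterion for the desired profile may also exist in redacted text or in the ultrasound SOP.

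**Conclusion.** The concern holds in a limited form. The OsciPulse–IPC paired t-test does not by itself establish that OsciPulse creates reversing flow. A null result cannot separate two effective devices from two ineffective ones: it occurs about 95% of the time in either case when the devices are equal. A result favouring IPC is compatible with OsciPulse working. A result favouring OsciPulse shows more flow than on IPC, not more than at rest. The visible text collects what is needed to answer the question directly, but does not clearly specify an OsciPulse-against-rest estimate, a confidence interval or a criterion for the profile.

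The conclusion rests on logic. The 93% and the power figures depend on the assumed SD, correlation, effect size and alpha. The weight is modest, because the endpoint is secondary and the comparative test is right for its own objective.

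**What to change.** - In Sections 9.2.2, 9.2.4 and 9.2.6, base the statement that OsciPulse creates reversing flow on the within-subject change (inflation minus rest) in reversing-flow volume on OsciPulse, with a 95% confidence interval. Say in 9.2.4 what the change is measured from.
- Name reversing-flow volume as the measure that carries this claim, with the other parameters supportive.
- Use every subject with an OsciPulse scan, whether or not there is an IPC scan, and amend Section 9.3 to permit it. As written, 9.3 would exclude subjects who did not complete both exposures and the required scans.
- Optionally, add the proportion of subjects meeting a profile fixed before the blinded reading, with an exact interval. If the ultrasound SOP already holds a criterion, cite it. Presence during inflation alone is not enough, since flow already present at rest would count.
- Keep the OsciPulse–IPC paired t-test for the comparative objective in Section 3.2.

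The cost is revised wording in four sections and a little more analysis of scans already planned. No scan, visit or subject is added.

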1 STUDY SUMMARY

Title	A phase 2, randomized study of the tolerability and safety of the OsciPulse device for the prevention of VTE
Short Title	OsciPulse tolerability trial
Phase	Phase 2
Methodology	Randomized, crossover study
Study Duration	4 months
Study Center(s)	Penn Presbyterian Medical Center
	Part 1:
	Primary
	
• To determine the tolerability of the OsciPulse device on healthy individuals.
	Secondary:
	
• To determine the hemodynamic impact of the OsciPulse device on venous blood flow.
	Part 2:
	Primary:
Objectives	
• To determine the tolerability and safety of the OsciPulse device• To evaluate device design with respect to initial clinical safety and device functionality.
	Secondary:
	
• To assess the compliance of the OsciPulse device compared to a standard intermittent pneumatic compression device.• To evaluate the ultrasonographic hemodynamic parameters of the OsciPulse device compared to a standard intermittent pneumatic compression device.

Number of Subjects	Part 1: Three (3) subjects at a single site. Part 2: Fifteen (15) to Twenty (20) subjects at a single site.
Study Population	Part 1: Adults age \geq 40 years healthy volunteers. Exclusion criteria include a current foot or ankle injury, current vascular disease. Part 2: Adults age \geq 18 years admitted to the hospital. Exclusion criteria include contraindications for pneumatic devices, current or previous DVT, and pregnancy.
Investigational Product	OsciPulse mechanical therapy device for the prevention of VTE
Participant Duration	Part 1: Up to 3 hours Part 2: Up to 6-hours in hospital
Description of Facilities	Part 1: Enrollments will take place in the [REDACTED] offices clinical research space. Part 2: Enrollments will take place at the Penn Presbyterian Medical Center (PPMC). [REDACTED] coordinators will conduct bedside data collection in the hospital setting, and chart reviews will be conducted in the [REDACTED] office space located on the [REDACTED] [REDACTED] [REDACTED] at PPMC. This office space is locked with a front door security code.
Reference therapy	Intermittent pneumatic compression device

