2.1 Study Rationale

Venous thromboembolism (VTE) is a major complication occurring in hospitalized subjects. Although anticoagulants and mechanical prophylaxis are commonly used to prevent VTE it remains a leading cause of complications and death in the hospital population. Anticoagulation has been demonstrated to reduce the rates of hospital acquired VTE, but also has increased rates of bleeding complications. Mechanical prophylaxis is typically used together with anticoagulation and has no bleeding risk. However, existing methods of mechanical thromboprophylaxis have some limitations including equivocal efficacy and subject discomfort, which may undermine adherence. The new OsciPulse device was designed based on recent advancements in our understanding of the molecular basis of deep vein thrombosis (DVT) formation to improve the efficacy of mechanical devices in preventing DVT/VTE. The objective of this study is to evaluate device design with respect to initial clinical safety and device functionality.

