4.6 Study Endpoints

4.6.1 Primary Study Endpoints

The primary endpoint will be subject safety and tolerability. Safety will be evaluated by the presence of adverse events (See section 10) during the intervention. Tolerability will be evaluated by a subject reported questionnaire. Tolerability will be measured by the 100-mm visual analog scale (VAS) and through open ended question answers. The average distance on the VAS in each domain of the questionnaire will be compared between the OsciPulse device and standard IPC.

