6.7 Administration and Accountability

The OsciPulse Instructions for Use will be provided to each subject and available in room for clinical staff. In summary, to administer the OsciPulse device, the calf bands will be fitted to the subject's calf with the aim to be snug without being too tight to restrict blood flow. [REDACTED]
[REDACTED].
[REDACTED]

[REDACTED] The clinical staff applying the device should confirm the first inflation to ensure that the device is set up correctly.

A pair of calf bands will be used for each subject, and at the end of the 3-hour period the bands will be disposed of in the hospital waste stream. The head unit can be wiped down with antiseptic wipes and returned to central storage along with the tubing.

The [REDACTED] staff will maintain accountability records for both the head units and the bands. The accountability log will include the following:

- the date of receipt of each item
- the unique identifiers of each item
- the date each device is distributed
- the protocol defined subject number to which each device was assigned
- Date of return or destruction

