6.8 Product Problems and Complaints

The study staff will record any product problems and complaints on the IP Quality Complaint form and notify [REDACTED] and the Sponsor according to section 10.4.3.

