8.5 Hemodynamic ultrasonography

A hemodynamic ultrasonography will be performed (when feasible) by certified technician/radiologist or physician trained in venous valve sinus imaging. The study specific ultrasound procedure SOP will be followed. All efforts will be made to conduct the ultrasound procedure with the assigned device even if subject is no longer clinically wearing the assigned device but agrees to wear for ultrasound procedure.

The following parameters will be measured both at rest and during the inflation period of the OsciPulse device and the calf ICD: centerline flow velocity, centerline flow, [REDACTED]

Video clips of the 2D color Doppler exams will be collected by the imaging personnel and transferred via a data storage device to [REDACTED] study personnel. The data will then be blinded and sent to Dr. [REDACTED], an expert in ultrasound image quantification, to perform the analysis and quantify the above parameters which will be provided back to the [REDACTED] team for data entry.

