10.3.1 Follow-up report

If an SAE/UADE has not resolved at the time of the initial report and new information arises that changes the investigator’s assessment of the event, a follow-up report including all relevant new or reassessed information (e.g., concomitant medication, medical history) should be submitted.

The investigator is responsible for ensuring that all SAEs are followed until either resolved or stable.

10.3.2 *Investigator Reporting: Local Reporting Requirements*

The investigator will adhere to local regulatory reporting requirements including the IRB/EC of record reporting requirements as well as IRB reporting requirements per 21 CFR 812. These additional reporting requirements include: failure to obtain informed consent, UADEs, device recall/repair/disposal, change in risk determination, or FDA or IRB withdrawal of the study.

10.4 *Investigator Reporting: Notifying the study Sponsor*

The following shall be reported to the Sponsor and Medical Director within 24 hours.

10.4.1 *SAE and UADE*

Every SAE and UADE regardless of suspected causality (e.g., relationship to study product(s) or study procedure(s) or disease progression) must be reported to the sponsor within **24 hours** of learning of its occurrence.

Recurrent episodes, complications, or progression of the initial SAE must be reported to the Sponsor as a follow-up to the original episode within 24 hours of the investigator receiving the follow-up information. A SAE considered completely unrelated to a previously reported one should be reported separately as a new event.

New information regarding the SAE will be reported as it becomes available and in the same manner that the initial SAE (i.e. SAE form). The investigator must follow the event to resolution or until the event is deemed and documented irreversible, whichever is longer.

10.4.2 *Failure to Obtain Informed Consent and Withdrawal of IRB Approval*

The PI must report to the Sponsor within 24 hours if informed consent is not obtained for any subjects enrolled on the trial or if the IRB withdraws approval of the study.

10.4.3 *Product Complaints*

OsciPulse device imperfections, malfunctions, or service required shall be reported to [REDACTED] and the Sponsor on the IP Quality Complaint Form. [REDACTED] will arrange for service or replacement of products for trial use.

10.4.4 *Protocol Deviations*

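### Section 9.2.2 reads deployment by clinical staff from flow scans that may use a device put on only for the scan, and set-up, malfunctions and device-reason removals have no planned summary

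*Combined protocol and SAP*

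**What the plan says.** **The conclusion.** Section 9.2.2 plans a paired t-test on the hemodynamic parameters and then states: "Confirming this flow in the subject population will demonstrate that the OsciPulse device can be successfully deployed in the clinical setting by clinical staff".

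**How the scan is made.** Section 8.5 asks that all efforts be made to scan with the assigned device "even if subject is no longer clinically wearing the assigned device but agrees to wear for ultrasound procedure".

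**The objective.** The Study Summary lists among the Part 2 primary objectives: "To evaluate device design with respect to initial clinical safety and device functionality". Section 2.1 repeats it as the aim of the whole study: "The objective of this study is to evaluate device design with respect to initial clinical safety and device functionality". Section 3.1 does not carry it. Section 4.6.1 says "The primary endpoint will be subject safety and tolerability". The secondary endpoints in 4.6.2 are wear time and flow.

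**What is observed about set-up and reliability.**
- Section 6.7: "The clinical staff applying the device should confirm the first inflation to ensure that the device is set up correctly".
- Section 6.8: "The study staff will record any product problems and complaints on the IP Quality Complaint form".
- Section 10.4.3: "OsciPulse device imperfections, malfunctions, or service required shall be reported to" a redacted party and the sponsor.
- Section 8.8: if the subject reports that a device was removed, staff note why and for how long.

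**Who is analysed.** Section 9.2 defines evaluable subjects as those who completed 6 hours, with 3 hours on each therapy. Section 9.3 limits the analysis to subjects with the required exposures, questionnaires and scans, and leaves out everyone else.

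**The concern.** The sentence in 9.2.2 names who deploys the device and where. Flow seen on a device put on for the scan shows that the device can generate the reversing flow in a patient. It does not show that the fit made for the 3-hour period was generating that flow. If the band had been misfitted, had slipped, or had been taken off for discomfort, the subject could still contribute a favourable scan.

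The observations that bear more directly on deployment are the first-inflation check, the complaint form and the removal reasons. None of them is an endpoint in 4.6, and none is summarised in section 9.

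At stake are a written conclusion that could be drawn when routine deployment had failed, and the set-up and reliability part of a stated objective, which would end without a reported result. The tolerability comparison is not affected.

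**Working it through.** **1. The plan's own figure.** Section 9.2.3 allows up to 6 losses among 20 enrolled: 20 − 6 = 14 evaluable. This reproduces. It is a convenience sample with no stated effect size, SD, alpha or power, and the point does not depend on any of these.

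**2. Does flow imply deployment by clinical staff?** Three things would have to be known for each scan.
- *Was the device as worn?* Section 8.5 permits either state, and no field to separate them is required in the text provided.
- *Who applied it?* Section 4.2.2 uses the passive voice for Part 2. Section 6.7 speaks of clinical staff applying the device, but the five accountability-log items listed there do not include the person who did so. Section 8.5 does not say who puts the device back on.
- *What counts as confirmed?* Sections 9.2.2 and 9.2.6 plan a paired t-test on between-device differences. No criterion per subject is given, so a favourable mean can coexist with individual failures.

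The inference therefore cannot be checked from the data that the text requires.

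**3. What is analysed and what is not.**

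| Aspect of functionality | Planned analysis |
|---|---|
| Flow generation | Paired t-test (9.2.2, 9.2.4, 9.2.6) |
| Wear time | Secondary endpoint (4.6.2); paired t-test in the synopsis; not carried into section 9 |
| First inflation confirmed | None; the check is asked for, but not stated to be recorded |
| Malfunctions and complaints | None; recorded and reported only |
| Reason for removal | None; noted only |

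**4. Effect of the analysis set.** This illustration assumes that 3 of 20 deployments fail and that those subjects do not complete. Under 9.3 they are not analysed.
- Success among those analysed: 17/17 = 100%.
- Success among all devices applied: 17/20 = 85%, exact 95% CI 62.1% to 96.8%.

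The plan computes no such proportion. The example shows only why a deployment summary must not be built on the 9.3 population.

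**5. What a descriptive summary could support.** With 0 failures in N, the exact two-sided 95% upper limit is 1 − 0.025^(1/N).
- N = 14: 23.2%
- N = 15: 21.8%
- N = 20: 16.8%

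With 1 failure in 20 the exact interval is 0.1% to 24.9%. With 3 in 20 it is 3.2% to 37.9%.

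The chance of seeing at least one failure is 1 − (1 − p)^N, for assumed true rates p:

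| p | N = 14 | N = 20 |
|---|---|---|
| 5% | 51% | 64% |
| 10% | 77% | 88% |
| 20% | 96% | 99% |

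Such a summary can reveal a common problem. It cannot rule out a moderate one.

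**The case against.** The strongest reply is that the sentence claims only that the device can be deployed, and that flow is itself a fair reading of functionality. Much of this stands. Flow generation is tested, and wear time is an endpoint. A reader might infer that the functionality data are not analysed at all, or that the objective goes wholly unanswered. The documents do not support that. They also disagree on whether functionality is a primary objective, since 3.1 leaves it out.

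Further points that stand:
- A reader might want to say by how many percentage points deployment success is overstated. The plan computes no success rate, and gives no share of re-applied scans, so any such figure would be invented.
- Re-application is not in itself a sign of failure. Section 6.2 provides for removal when the subject walks or needs care, and clinical staff may be the ones who put the device back on.
- A device that had broken would produce no flow at the scan unless repaired or replaced, so the scan would expose that kind of failure.
- The Ultrasound SOP and the Instructions for Use were not available, and 6.7 and 8.5 contain redactions. They may say who applies the device for the scan, or require its status to be noted.
- Restricting the conclusion to as-worn scans would drop the subjects who had taken the device off, and could make the result look better.

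What does not stand is the capability reading as a full defence, because the sentence specifies clinical staff and the clinical setting. Nor does the 3-hour exposure requirement rescue it. Read strictly, that requirement removes early removers from the analysis, so failures disappear instead of being counted.

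**Conclusion.** The concern holds in a bounded form. The scans can support a statement that OsciPulse produces its intended flow in hospital patients. They cannot, as planned, support a statement that clinical staff deployed it successfully during the 3-hour period. Separately, set-up success, malfunctions and device-reason removals have no endpoint or summary, although two places in the protocol name functionality as an objective.

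The size of any error in the deployment statement cannot be derived from the documents. It depends on how many scans use a re-applied device and on how often the as-worn fit was inadequate, and neither is given. The conclusion rests on the text provided and would soften if the SOP or Instructions for Use already require the missing fields. No primary analysis or decision rule depends on the sentence. It should still be settled before data collection, because as-worn status and the applier's role cannot be reliably recovered afterwards.

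**What to change.** 1. **At each scan**, record whether the device was as worn or re-applied for the scan, and the role of the person who applied it. Keep all scans in the paired device comparison.
2. **In 9.2.2**, either limit the sentence to flow generation, or base the deployment statement on every OsciPulse period in which the device was applied. In the second case, count set-up failure, malfunction or removal for a device reason as not successful instead of dropping the subject, and report as-worn flow separately. Removals that 6.2 already provides for, for walking or care, are not failures.
3. **In 4.6 and 9.2**, add a descriptive summary over all applied OsciPulse periods, not only the 9.3 population. Give n/N with an exact 95% CI for first inflation confirmed (this needs a recorded field), no malfunction on the complaint form, and no device-reason removal.
4. **Align the objectives** in the synopsis, 2.1 and 3.1.

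The cost is about three extra data fields, one table and some wording, with no added visits or subjects. The downsides are a deployment statement that may look less favourable and the wide intervals shown above, which is why the summary should be descriptive. Removal reasons also rest on what subjects report.
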